6.2. Exclusion Criteria

Patients meeting any of the following criteria are not eligible for study participation:

1. Weight gain $>5\%$ in the previous 3 months.
2. Weight loss $\geq 2\%$ in the previous 3 months.

NOTE: Dietary and/or exercise regimens, with or without the use of medications, supplements or herbal treatments associated with weight loss (eg, orlistat, lorcaserin,

phentermine, topiramate, naltrexone, bupropion, glucagon-like peptide-1 [GLP-1] receptor agonists, etc.) are allowed if:

- the regimen and/or dose has been stable for at least 3 months prior to randomization
- the patient has not experienced weight loss $\geq 2\%$ during the previous 3 months, AND
- the patient intends to keep the regimen and/or dose stable throughout the course of the study.

3. Bariatric surgery or procedure (eg, gastric bypass/band/sleeve, duodenal switch, gastric balloon, intestinal barrier, etc.) within the last 6 months. All patients with a history of bariatric surgery or procedures must be discussed with, and receive approval from, the Sponsor prior to enrollment.
4. Diagnosis of severe psychiatric disorders (eg, schizophrenia, bipolar disorder, personality disorder), or Major Depressive Disorder (MDD) within the previous 2 years, or Screening Patient Health Questionnaire (PHQ)-9/PHQ-A score ≥ 15 , or any suicidal ideation of type 4 or 5 on the Columbia-Suicide Severity Rating Scale (C-SSRS) during Screening, or lifetime history of suicide attempts, or any suicidal behavior in the last month.
5. HbA1c $> 10.0\%$ at Screening.
6. Current, clinically significant pulmonary, cardiac, or oncologic disease considered severe enough to interfere with the study and/or confound the results. Any patient with a potentially clinically significant disease should be reviewed with the Sponsor to determine eligibility.
7. Glomerular filtration rate (GFR) $< 30 \text{ mL/min}/1.73 \text{ m}^2$ during Screening.
8. Significant dermatologic findings relating to melanoma or pre-melanoma skin lesions (excluding non-invasive basal or squamous cell lesion), determined as part of a comprehensive skin evaluation performed by the Investigator during Screening. Any concerning lesions identified during Screening will be biopsied and results known to be benign prior to enrollment. If the pre-treatment biopsy results are of significant concern, the patient is not eligible for study participation.
9. History or close family history (parents or siblings) of skin cancer or melanoma (not including noninvasive, infiltrative basal or squamous cell lesion), or patient history of ocular-cutaneous albinism.
10. Participation in any clinical study with an investigational drug/device within 3 months or 5 half-lives, whichever is longer, prior to the first setmelanotide dose.
11. Previously enrolled in a clinical study involving setmelanotide or any previous exposure to setmelanotide.
12. Inability to comply with QD injection regimen.
13. Pregnant and/or breastfeeding, or desiring to become pregnant during this trial.
14. Cognitive impairment that, in the Investigator's opinion, precludes participation to the study and completions of study procedures or questionnaires.
15. Patient is, in Investigator's opinion, otherwise not suitable to participate in the study.

6.3. Lifestyle Restrictions

There are no lifestyle restrictions during study participation.

6.4. Screen Failures

Screen failures are defined as patients who consent to participate in the clinical study but are not subsequently enrolled. A minimal set of screen failure information is required to ensure transparent reporting of screen failure patients to meet the Consolidated Standards of Reporting Trials publishing requirements and to respond to queries from regulatory authorities. Minimal information includes demography, screen failure details, eligibility criteria, and any serious adverse event (SAE).

Individuals who do not meet the criteria for participation in this study (screen failure) may be eligible for rescreening at a later date, depending on the reason for the initial screen failure and provided enrollment is still open. Rescreening of a patient must be approved by the Sponsor prior to rescreening. If a patient is approved for rescreening by the Sponsor, the rescreened patients should be assigned the same Screening number as for the initial screening. Up to 3 screenings per patient are allowed (2 screening failures).

7. TREATMENTS

Study treatment is defined as any investigational treatment(s), marketed product(s), placebo, or medical device(s) intended to be administered to a study patient according to the study protocol.

7.1. Treatments Administered

All patients will receive open-label setmelanotide in this study.

Setmelanotide will be supplied by Rhythm.

Setmelanotide drug product is a preserved, multidose solution for injection to be administered SC, QD. It is formulated as a 10 mg/mL sterile, preserved, clear to slightly opalescent, colorless to slightly colored solution, practically free of visible particles. The drug product solution (1 mL) is presented in a clear 2R glass vial with a rubber stopper.

Packaging and labeling will be prepared to meet all regulatory requirements.

Setmelanotide will be administered as SC injection QD.

7.2. Method of Treatment Assignment

All patients will receive setmelanotide in this study. The starting setmelanotide dose is dependent on patient age at the time of Visit 2 (Day 1); however, for all patients, the setmelanotide dose will be titrated to a final dose of 3.0 mg/day (initial titration phase), as follows:

Patients aged 6 to <16 years

- Starting at Baseline (Day 1; Visit 2) through approximately Day 14, patients will receive setmelanotide 1.0 mg/day.

- Starting at approximately Day 15 through 28, patients will receive setmelanotide 2.0 mg/day.
- Patients/caregivers will be contacted by study center personnel on Day 15 to ensure dose titration has occurred and to document any AEs.
- Starting on approximately Day 29 (Visit 3), patients will receive setmelanotide 3.0 mg/day; patients will continue to receive setmelanotide 3.0 mg/day for 12 weeks.

The dose of setmelanotide should be titrated as explained in the SoA.

Patients aged ≥16 years

- Starting at Baseline (Day 1; Visit 2) through approximately Day 14, patients will receive setmelanotide 2.0 mg/day.
- Starting at approximately Day 15, patients will receive setmelanotide 3.0 mg/day; patients will continue to receive setmelanotide 3.0 mg/day for 14 weeks.

The dose of setmelanotide should be titrated as explained in the SoA.

7.3. Dose Modification

The intention of the study is for all patients to reach a dose of 3.0 mg per day. If a patient experiences tolerability or safety issues during the dose titration phase, a lower maintenance dose may be used during the trial, with approval by the Sponsor. Additionally, after titration to a dose of 3.0 mg is complete, the setmelanotide dose should not be lowered unless discussed and approved by the Sponsor. No dose greater than 3.0 mg per day will be used in this study.

7.4. Blinding

This is an open-label study; no blinding methods will be employed.

7.5. Preparation/Handling/Storage/Accountability

Only patients enrolled in the study may receive study treatment and only authorized site staff may supply or administer study treatment. All study treatments must be stored in a secure, environmentally controlled, and monitored (manual or automated) area in accordance with the labeled storage conditions with access limited to the Investigator and authorized site staff.

All study drug must be kept in a secure, limited-access storage area at a temperature between 2°C to 8°C. Setmelanotide is stable at room temperature for a short time period that will allow patients to transport study drug home; ice packs and cooler bags will be provided for patients and caretakers who will travel long distances from the clinic. Once home, the un-opened study drug must be stored in the patient's refrigerator. Opened study drug may be stored at room temperature for up to 30 days.

There will be extensive training of patients in drug administration including educational materials. Study specific training materials will be provided to both the investigative staff and study patients and caregivers.

7.6. Assessment of Treatment Compliance and Study Drug Accountability

Accountability for the study drug at the study site is the responsibility of the Investigator. The Investigator will ensure that the study drug is used only in accordance with this protocol. Where allowed, the Investigator may choose to assign drug accountability responsibilities to a pharmacist or other appropriate individual. Drug accountability records indicating the delivery date to the site, inventory at the site, use by each patient, return of all used study drug to the study center, and return to Rhythm (or disposal of the drug, if approved by Rhythm) will be maintained by the clinical site. Reasons for departure from the expected dispensing regimen must also be recorded. The Sponsor or its designee will review drug accountability at the site during monitoring visits.

Compliance to dosing will be monitored throughout the study by having the patient complete a daily dosing log that records daily dosing information, including whether the dose was administered, and if not administered, the rationale for why it was not administered. If a patient is non-compliant with the dosing schedule, the Sponsor may implement steps to ensure compliance, eg, sending a nurse to the patient's home for retraining or having a nurse administer the study drug.

7.7. Concomitant Therapy

Any medication or vaccine (including over-the-counter or prescription medicines, vitamins, and/or herbal supplements) that the patient is receiving at the time of enrollment or receives during the study must be recorded along with:

- Reason for use
- Dates of administration including start and end dates
- Dosage information including dose and frequency

The Medical Monitor should be contacted if there are any questions regarding concomitant or prior therapy.

7.7.1. Prohibited Medications

Unless concomitant medications are likely to present a strong potential safety concern, the general goal of this protocol is to allow as many patients with this rare condition to participate in the study as possible.

However, patients are not permitted to enter the study if they have had weight gain $>5\%$ during the previous 3 months or $>2\%$ weight loss during the prior 3 months. It should be noted that dietary and/or exercise regimens, with or without the use of medications, supplements or herbal treatments associated with weight loss (eg, orlistat, lorcaserin, phentermine, topiramate, naltrexone, bupropion, glucagon-like peptide1 [GLP1] receptor agonists, etc.) are allowed if:

- the regimen and/or dose has been stable for at least 3 months prior to randomization
- the patient has not experienced weight loss $\geq 2\%$ during the previous 3 months, AND

- the patient intends to keep the regimen and/or dose stable throughout the course of the study.

GLP-1 receptor agonists may be used up to the dose approved for the treatment of diabetes mellitus (eg, liraglutide up to a daily dose of 1.8 mg) as long as (1) it is not being prescribed for the treatment of obesity, (2) the dose has been stable for at least 3 months prior to enrollment, (3) the patient has not experienced >3% weight loss during the previous 3 months, AND (4) the patient intends to keep the dose stable throughout the course of the study.

Other medications that may cause weight loss (eg, stimulants) are allowed as long as the patient (1) has used a stable dose for at least 3 months prior to enrollment, (2) has not lost weight during the previous 3 months, and (3) intends to keep the dose of the medication stable through the course of the study.

All concomitant medications should be kept at a stable dose throughout the course of the study, unless a dose change is necessary to treat an AE.

7.8. Treatment after the End of the Study

After the EOS Visit, no further treatment is planned under the auspices of this protocol. Patients who meet the primary endpoint of this study may be eligible to enroll in a separate long-term extension study under which auspices the patient would continue to receive setmelanotide.

8. DISCONTINUATION/WITHDRAWAL CRITERIA

Given this rare patient population, every effort will be made to encourage and keep patients enrolled in the study until completion, unless there are any safety concerns necessitating withdrawal of the patient. Rhythm will provide assistance for any patient and caregiver travel, will make available visiting home health care professionals, and any other necessary logistical support to ease the burden on the patient in order to facilitate compliance.

If the patient withdraws consent for disclosure of future information, the Sponsor may retain and continue to use any data collected before such a withdrawal of consent.

If a patient withdraws from the study, he/she may request destruction of any samples taken and not tested, and the Investigator must document this in the site study records.

Patients will be informed that they have the right to withdraw from the study at any time for any reason, without prejudice to their medical care. The Investigator also has the right to withdraw patients from the study, after discussion with the Sponsor, for reasons such as:

- AEs, which justify treatment or study withdrawal. For specific predefined events, additional monitoring and guidance for the Investigator is provided in [Appendix 6](#).
- Non-adherence to study drug regimen or protocol requirements.
- Non-compliance with instructions or failure to return for follow-up.

9. PATIENT ASSESSMENTS

Study procedures and their timing are summarized in the SoA ([Table 1](#)). Adherence to the study design requirements, including those specified in the SoA, is essential and required for study conduct.

All screening evaluations must be completed and reviewed to confirm that potential patients meet all eligibility criteria. The Investigator will maintain a screening log to record details of all patients screened and to confirm eligibility or record reasons for screening failure, as applicable.

When scheduled at the same time point, the order of procedures should be as follows: obtain vital signs, perform 12-lead electrocardiogram (ECG), and perform blood draws (at the specified time point, if applicable). Adjustments may be made depending upon specific circumstances and in consultation with the Sponsor.

Immediate safety concerns should be discussed with the sponsor immediately upon occurrence or awareness to determine if the patient should continue or discontinue study treatment.

9.1. Informed Consent/Accent

A complete description of the study is to be presented to each potential patient, and signed and dated informed consent and/or assent is to be obtained before any study-specific procedures are performed.

Procedures conducted as part of the patient's routine clinical management (eg, blood count) and obtained before signing of the informed consent form (ICF) may be utilized for Screening or Baseline purposes provided the procedures met the protocol-specified criteria and were performed within the time frame defined in the SoA.

9.2. Inclusion/Exclusion Review

Inclusion and exclusion criteria are to be reviewed per the SoA ([Table 1](#)) to ensure the patient is eligible for the study.

9.3. Demographics, Concomitant Medications and Medical History Review

Medical history and demographic data including the patient's gender, race, date of birth, and concomitant medication use will be obtained for all patients during the Screening Period ([Table 1](#)).

The medical history should be updated on Day 1 prior to first dose of study drug, to assess continued study eligibility and adherence to final inclusion/exclusion criteria. This medical history update includes a review for changes from Screening as well as a review of the patient's recent medication use to assess whether any changes have occurred since the previous visit.

9.4. Type of Lesions on Magnetic Resonance Imaging

All patients must have evidence of hypothalamic injury on MRI completed within 8 months of Screening. If no MRI is available, then it may be repeated during the Screening Period.

Hypothalamic Lesion score [Roth 2015] will be noted and collected for each patient when possible.

9.5. Height

For patients ≥ 18 years of age, height needs to be measured at Screening only. For patients aged < 18 years, height is to be measured at the time points designated in the SoA ([Table 1](#)).

Height (cm) will be measured, without shoes, socks, or hats, using a wall-mounted stadiometer. All measurements will be done in triplicate at each time point and recorded to the nearest half cm.

9.6. Weight

Weight (kg) will be recorded at the time points designated in the SoA ([Table 1](#)). Weight (kg) is to be measured at the clinic using the same scale throughout the study, including the Screening Visit, after patients have emptied their bladders and pockets and after fasting for at least 8 hours. Patients are to wear light clothing or underwear and no shoes, and will be weighed at approximately the same time of day. Weight should be recorded to the nearest tenth of a decimal place if reported by a digital scale or to the nearest half of a kg if reported by a mechanical scale.

The scale should be calibrated on a regular basis per the manufacturer's specifications.

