6. Weight (kg) is to be measured at the clinic using the same scale throughout the study, including the Screening Visit, after patients have emptied their bladders and pockets and after fasting for at least 8 hours. Patients are to wear light clothing or underwear and no shoes, and will be weighed at approximately the same time of day. Weight should be recorded to the nearest tenth of a decimal place if reported by a digital scale or to the nearest half of a kg if reported by a mechanical scale.
7. Waist circumference (cm) will be done in triplicate and recorded to the nearest half cm. Waist circumference should be measured after patients have fasted for at least 8 hours and at approximately the same time at each visit. Patients should be standing and in light clothing and have emptied their bladder. Whenever possible, the same study staff member should perform the measurement for a given patient to minimize variability.
8. For patients ≥ 18 years of age, height needs to be measured at Screening only. Height (cm) will be measured, without shoes, socks, or hats, using a wall-mounted stadiometer. All measurements will be done in triplicate at each time point and recorded to the nearest half cm.
9. Body composition assessment will be performed using DXA. If DXA is not available at the clinic, this procedure may be skipped, with prior approval of the Sponsor.
10. All blood pressure (BP) and heart rate (HR) measurements are to be obtained with the patient in the sitting position following at least 5 minutes of rest. All measurements will be taken in triplicate, approximately 2 minutes apart. When possible, BP should be taken in the non-dominant arm throughout the study, using the same methodology (automated or manual). Body temperature ($^{\circ}\text{C}$) and respiration rate (breaths/minute) will be obtained in the sitting position following at least 5 minutes of rest.
11. A single 12-lead ECG will be performed in the supine position following a period of at least 10 minutes of rest. At V2, the ECG will be performed before and 4 hours after dosing, and at V3 and V6, the ECG is to be performed at 4 hours after dosing.
12. A urine pregnancy test may be performed to expedite availability of results prior to dosing on Day 1. All other pregnancy tests will be serum tests; dosing may continue with results pending.
13. Collected prior to study drug administration.

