### 3.5 Patient Assessments

#### 3.5.1 Vital Signs

Vitals signs include:

- Height (cm)
- Weight (kg)
- Waist circumference (cm)
- Temperature (C)
- Heart Rate (beats/min)
- Systolic Blood Pressure (mmHg)
- Diastolic Blood Pressure (mmHg)
- Respiratory Rate

Vital signs will be assessed from screening and at every post-baseline visit. Patients 18 years or older will only have height measured at screening. Height, weight, heart rate, systolic blood pressure, and diastolic blood pressure will be measured in triplicates at each visit. In addition to the individual measurements the above items will be aggregated into a mean value per visit (i.e. mean of all height measurements).

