## 9.1 Primary Efficacy Endpoint

The primary endpoint is defined as the proportion of patients who achieve at least 5% BMI reduction from baseline, at ~16 weeks of treatment with setmelanotide. BMI will be calculated using patient's weight and height assessments, using the following formula:

$$BMI = \frac{kg}{m^2}$$

If needed, weight and height will first be converted into kilograms and meters, respectively. Given that body weight is collected in triplicates at each visit, weight (kg) will first be aggregated into one averaged weight per visit. Visits will then be compared against the analysis visit window (described in [Section 4.2](#)) to select the Week 16 averaged weight prior to calculating BMI and change in BMI. Patients who are  $\geq 18$  years of age will only have height measurement done at screening; the averaged triplicate

screening height will be used for the height component of the BMI calculation at each visit. Patients who are < 18 years of age will have their height measured in triplicates at most study visits. As with body weight, height will first be aggregated into one averaged height per visit and compared against the analysis visit window to select the Week 16 averaged height. Regardless of reason, if height is missing for an analysis visit, then height will be imputed using last observation carried forward (LOCF). Change ( $\Delta$ ) in BMI (%) from baseline at 16 weeks of treatment will be calculated as follows:

$$\Delta \text{ BMI } (\%) = \left( \frac{\text{Week 16 BMI} - \text{Baseline BMI}}{\text{Baseline BMI}} \right) * 100$$

An indicator variable will then be created to identify patients that have a decrease in BMI from baseline to Week 16 of 5% or more, allowing for the analysis of proportion of patients who achieve at least 5% BMI reduction.

The primary endpoint will be assessed using an exact binomial test at a 1-sided 0.05 significant level, compared to the null hypothesis proportion of 0.05 (which comes from a historical control rate of 5%). The number of and the binomial proportion of patients who achieve at least 5% BMI reduction from baseline at 16 weeks, the corresponding 2-sided 90% CI, and one-sided binomial test p-value will be presented. The Clopper-Pearson method will be used to calculate the CI. A scatter plot figure will also be created plotting each patient's percent BMI reduction from baseline to Week 16.

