5. A comprehensive skin examination will be performed by the Investigator. The skin examination should include a full body (head-to-toe skin examination). If any concerning lesions are identified during Screening, the patient should be referred to a dermatologist. Any concerning lesions will be biopsied by the dermatologist and results must be benign prior to the first dose of setmelanotide. If the pre-treatment biopsy results are of concern, the patient will be excluded from the study. Additionally, any concerning lesion or change in an existing lesion during the course of the study must be evaluated by the dermatologist and biopsied, if clinically indicated in the opinion of the dermatologist.
6. Weight (kg) is to be measured at the clinic using the same scale throughout the study, including the Screening Visit, after patients have emptied their bladders and pockets and after fasting for at least 8 hours. Patients are to wear light clothing or underwear and no shoes, and will be weighed at approximately the same time of day. Weight should be recorded to the nearest 10th of a decimal place if reported by a digital scale or to the nearest half of a Kg if reported by a mechanical scale.
7. Waist circumference (cm) will be done in triplicate and recorded to the nearest half cm. Waist circumference should be measured after patients have fasted for at least 8 hours and at approximately the same time at each visit. Patients should be standing and in light clothing and have emptied their bladder. Whenever possible, the same study staff member should perform the measurement for a given patient to minimize variability.
8. For patients ≥18 years of age, height needs to be measured at Screening only. Height (cm) will be measured, without shoes, socks, or hats, using a wall-mounted stadiometer. All measurements will be done in triplicate at each time point and recorded to the nearest half cm.
9. Body composition assessment will be performed using DXA. If DXA is not available at the clinic, this procedure may be skipped, with prior approval of the Sponsor.

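### Half-kilogram weight recording is too coarse for a 5% BMI responder cut applied from age 6; record to 0.1 kg and reconcile the number of weight readings

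*Protocol*

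**What the plan says.** Protocol 9.6 sets out how to weigh the patient: fasted, bladder emptied, light clothing, about the same time of day, and "Weight (kg) is to be measured at the clinic using the same scale throughout the study". Resolution depends on the equipment. For a digital scale: "Weight should be recorded to the nearest tenth of a decimal place if reported by a digital scale" (Schedule of Activities, footnote 6; same rule in 9.6), which I read as 0.1 kg. For a mechanical scale: "to the nearest half of a kg if reported by a mechanical scale". The SAP's copy of the schedule (16.1, footnote 6) repeats the allowance: "to the nearest half of a Kg if reported by a mechanical scale".

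On the number of readings, Protocol 9.6 says only "Weight (kg) will be recorded at the time points designated in the SoA". Height is treated differently: "All measurements will be done in triplicate at each time point and recorded to the nearest half cm" (Protocol 9.5). Waist (9.7), blood pressure and heart rate (9.11) are also triplicate.

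SAP 3.5.1 states: "Height, weight, heart rate, systolic blood pressure, and diastolic blood pressure will be measured in triplicates at each visit". SAP 9.1 builds the primary endpoint on that premise: "Given that body weight is collected in triplicates at each visit, weight (kg) will first be aggregated into one averaged weight per visit". SAP 9.2.1 and 9.3.1 do the same for the other weight endpoints. The table of changes from the protocol (SAP 16.2) shows no entry on this.

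**The concern.** Weight is the numerator of BMI, so it drives the primary responder call and every other weight-based responder endpoint. A fixed 0.5 kg step is a larger fraction of a small child's weight than of an adult's, yet the same 5% cut applies to all. Up to 10 patients may be aged 6 to 12.

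Two things are at stake. First, a patient whose true change lies near 5% may be put on the wrong side of the cut by rounding alone. That matters for the count of responders and for the patient, because Protocol 5.1 makes a patient who meets the primary endpoint potentially eligible for the extension study. Second, the SAP averages a triplicate weight that the protocol does not ask sites to collect, so the two documents do not describe the same measurement.

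**Working it through.** The plan gives no figure for weighing error, so there is none to reproduce. Body weights and the spread of true loss are also not in the documents; they are assumptions below. Height is held fixed, so percent change in weight equals percent change in BMI.

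**Inputs from the documents.** Mechanical-scale step 0.5 kg, hence up to ±0.25 kg per recorded weight; digital step 0.1 kg, hence ±0.05 kg (Protocol 9.6). Responder: BMI fall of 5% or more (SAP 9.1). Exact binomial test, one-sided 0.05, null rate 5% (Protocol 10.3). About 15 patients (Protocol 5.2).

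**Step 1: largest shift.** Two roundings can move the difference by 2 × 0.25 = 0.5 kg. As a share of body weight: 0.5/25 = 2.0%; 0.5/30 = 1.67%; 0.5/50 = 1.0%; 0.5/100 = 0.5%.

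**Step 2: band of true loss in which a flip is possible.** With baseline weight W and rounding error e, the recorded call can differ from the true one when true loss lies between 1 − (0.95(W+e)+e)/W and 1 − (0.95(W−e)−e)/W, that is 5% ± 1.95e/W.

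| Assumed W | 0.5 kg step (e=0.25) | 0.1 kg step (e=0.05) |
|---|---|---|
| 25 kg | 3.05–6.95% | 4.61–5.39% |
| 30 kg | 3.38–6.63% | 4.67–5.33% |
| 50 kg | 4.03–5.98% | 4.81–5.19% |
| 100 kg | 4.51–5.49% | 4.90–5.10% |

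**Step 3: worked pairs.**
- 29.3 to 28.2 kg: −1.1/29.3 = −3.75%, a true non-responder. Recorded 29.5 to 28.0: −1.5/29.5 = −5.08%, a responder.
- 30.7 to 28.8 kg: −1.9/30.7 = −6.19%, a true responder. Recorded 30.5 to 29.0: −1.5/30.5 = −4.92%, a non-responder.

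**Step 4: share of calls that are wrong (simulation, every scale mechanical unless stated).**

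| Assumed true loss | 25 kg | 30 kg | 40 kg | 100 kg |
|---|---|---|---|---|
| Uniform 3–7%, 0.5 kg step | 13.6% | 16.0% | 12.0% | 4.8% |
| Uniform 3–7%, 0.1 kg step | 3.3% | 2.7% | 2.0% | 0.8% |
| Normal, mean 4%, SD 5 points, 0.5 kg step | 4.3% | 5.0% | 3.7% | 1.5% |
| Normal, mean 0, SD 4 points, 0.5 kg step | 2.5% | 3.0% | 2.3% | 0.9% |

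At 30 kg with SD from 3 to 8 points, the error is 2.0–2.8% for mean change 0 and 2.8–7.4% for a mean loss of 5%; with 0.1 kg recording it is 0.4–0.5% and 0.5–1.4%. Across such spreads at 25–40 kg the range is about 2–8%, against about 0.4–1.7%. The top of each range comes from a narrow spread (SD 3 points) centred near the cut. The uniform rows describe only patients whose true loss is already within 2 points of the cut.

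With the maximum of 10 patients aged 6 to 12, all at 25–40 kg and all on mechanical scales, that is 10 × 0.02 to 10 × 0.08, or 0.2 to 0.8 wrong calls expected.

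**Step 5: effect on the test.** At N=15 and rate 0.05, P(0) = 0.463, P(1) = 0.366 and P(2) = 0.135. So P(X≥2) = 1 − 0.829 = 0.171 and P(X≥3) = 0.036. At N=20, 3 responders give 0.076 and 4 give 0.016. One call can therefore decide the result when the count sits at the boundary.

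For type I error, take mean change 0 and SD 3 points, all patients near 30 kg and all on mechanical scales. The true rate is 4.8% and the recorded rate 5.5%. At that recorded rate P(X≥3) is 4.7% at N=15, and P(X≥4) is 2.2% at N=20. Both stay below 5%.

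**The case against.** The half-kilogram rule is conditional. Nothing in the documents says that any of the 3–5 US sites uses a mechanical scale, and if none does the rounding problem does not arise. Same-scale weighing, fasting and calibration already limit other error. Adults must have a BMI of at least 35, so they are probably heavy, where rounding matters least. Wrong calls go both ways and largely cancel: at 30 kg, with mean loss 4% and SD 5 points, the recorded response rate is 43.1% against a true 42.0%. Fragility to one call is a feature of any binary endpoint at N=15. At the 40% target, exactly 2 or 3 responders has probability of only 0.022 + 0.063 = 0.085. All of this stands, and it limits the point to individual calls.

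A reader might infer that the protocol prescribes a single weight, so that the SAP's average cannot be formed. The documents do not support that. Protocol 9.6 is silent on the number of readings, and SAP section 2 says the plan also rests on the case report forms, which are not available here and may already provide for three. Nor would the analysis fail with one reading, since the mean of one reading is that reading.

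What remains is that the protocol expressly permits a recording step that is coarse for its youngest patients, and that removing it is cheap. Same-scale use does not remove rounding. Triplicates alone do not either, because repeat readings on one scale can round to the same value.

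**Conclusion.** The point holds as a cheap improvement to the recording rule, with a separate reconciliation of the number of readings. Under the assumed weights of 25–40 kg and assumed spreads of true loss, half-kilogram recording misclassifies about 2–8% of patients weighed on a mechanical scale, and 0.1 kg recording cuts that about four- to six-fold.

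Two stronger readings are not supported. The 12–16% error at 25–40 kg is not a trial-wide rate: it requires every true loss to lie between 3% and 7%. Nor do the figures show an inflated type I error or a distorted response rate: in the scenario examined, type I error stays below 5%. The replicate mismatch taken alone is a documentation point.

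The result rests on body weights and loss distributions that the documents do not give, on fixed height, and on a mechanical scale being used. Height rounding is not included.

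**What to change.** In Protocol 9.6, footnote 6 of the Schedule of Activities and footnote 6 of the SAP's schedule (16.1), delete the half-kilogram option and require a calibrated digital scale recorded to 0.1 kg at every visit. Write 0.1 kg explicitly, since the present phrase for digital scales is loosely worded.

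Separately, make the number of readings agree. Either add triplicate weighing to the protocol, as for height and waist, or change SAP 3.5.1, 9.1, 9.2.1 and 9.3.1 to the single recorded weight. The 0.1 kg rule is needed under either choice.

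The cost is a wording change in both documents, and a digital scale at any of the 3–5 sites that has only a mechanical one. Triplicate weighing, if chosen, adds about a minute per visit.
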